## **7.5 SECONDARY OUTCOME(S)**

### **7.5.1 Key secondary outcome(s)**

This section is not applicable as no key secondary outcome has specified in the protocol.

### **7.5.2 (Other) Secondary outcome(s)**

Frequency and percentage of patients who require dose reductions, interruptions and discontinuation due to adverse events will be presented separately by system organ class and preferred term.

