At visit 1, the baseline characteristics (e.g. demographics, pulmonary function tests, HRCT evaluation etc., see [section 10.3.3](#)) will be recorded for all patients (either treated with nintedanib or pirfenidone).

The medical records of patients belonging to Group A and B will be evaluated to see if any ADRs and SAEs have occurred in the nintedanib treated arm during the duration of the treatment/ 52 weeks, whichever is earlier. Group B and Group C patients will be followed up according to clinical practice

for at least 52 weeks /discontinuation (whichever is earlier) from the start of the treatment at regular intervals (i.e. approximately every 4 weeks for the first 3 visits and approximately every 12 weeks thereafter till week 52). At each visit, all ADRs associated with nintedanib and SAEs will be recorded and reported per [section 12.2](#). In case a patient discontinues nintedanib before 52 weeks, all ADRs and SAEs will be collected till the date of discontinuation of nintedanib. There may be unscheduled visits between the scheduled visits. All ADRs and SAEs will also be collected at these unscheduled visits and entered into the eCRF. For nintedanib treated patients, certain information (e.g. co-medications, see [flowchart](#)) will also be collected at further and unscheduled visits (if available), as the status may change over time.

In case the patient is lost to follow up (patients not contactable for further visits), the site should attempt to contact the patient or patient's relative telephonically to gather the information on the vital status and record it in the eCRF.

Additionally, whenever the investigator becomes aware of SAEs and/or ADRs occurring in an enrolled patient before individual patient's end of study and it needs to be reported as per [section 12.2](#).

Patients who have taken at least one dose of nintedanib will be included in the safety analysis.

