10.5 SAMPLE SIZE

200 IPF patients treated with nintedanib according to approved Indian label (classified as Group A, B and C, see [section 10.1](#)) will be enrolled in this active surveillance program. The sample size of 200 is as per the request from the regulatory agency.

In addition 200 IPF patients who were treated with pirfenidone (classified as Group I, II and III, see [section 10.1](#)) at the same centres and during the same time frame will also be included. The baseline characteristic of these patients will be recorded at visit 1 and they will not be followed.

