10.7 DATA ANALYSIS

Analyses will be descriptive in nature including means, medians, standard deviation and interquartile range for continuous variables, and frequencies and percentages for binary and categorical variables with the corresponding 95% confidence intervals. For safety outcomes, incidence rates with corresponding 95% confidence intervals will be calculated. The baseline characteristics of 200 pirfenidone treated patients will be used to compare with the patients profile of the Nintedanib users. Whenever patient profiles differ between those treated with nintedanib and pirfenidone, cautious interpretation is required.

Subgroup analysis will be performed according to prior treatment (see [section 10.7.1](#)).

Any patient who meets the following criteria is treated as ineligible for safety analysis:

- Required registration procedure was not followed

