### **3 INTRODUCTION**

"As per ICH E9, the purpose of this document is to provide a more technical and detailed elaboration of the principal features of the analysis described in the protocol and to include detailed procedures for executing the statistical analysis of the primary and secondary variables and other data.

This TSAP assumes familiarity with the Clinical Trial Protocol (CTP) version 5.0, dated [REDACTED] and Case Report Form (CRF) version final 3.0, dated [REDACTED]. In particular, the TSAP is based on the planned analysis specification as written in CTP Section 10.7 'Data Analysis'. Also the 6 subjects (Subject ID: [REDACTED], [REDACTED]) enrolled in the study based on inclusion\exclusion criteria of protocol version 2.0, dated [REDACTED] and remaining subjects are on protocol version 5.0. Therefore, TSAP readers may consult the CTP for more background information on the study, e.g., on study objectives, study design and population, treatments, definition of measurements and variables, planning of sample size." This TSAP is to contain the analysis specification for a status report of the active surveillance to be submitted to DCGI annually and for the final analysis SAS® version 9.4 will be used for all analyses.

This is an active surveillance study and aim of this study to monitor the real world safety in Indian patients prescribed nintedanib for the treatment of Idiopathic Pulmonary Fibrosis (IPF). The scientific objective of this active surveillance is to obtain an estimate of the occurrence of all ADRs and SAEs in IPF patients prescribed nintedanib per the approved label in the real world setting. In addition, this study will also calculate the percentage of patients who require dose reductions, interruptions and discontinuation due to adverse events. This would help in assessing the safety of nintedanib in IPF patients in Indian real world setting.

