### **6.3 PATIENT SET ANALYSED**

➤ **Screened Set:**

Screened Set includes all patients who sign the ICF by either voluntarily or patient's legally authorized representative.

➤ **Entered Set:**

Entered Set includes patients in screened set who met the eligibility criteria.

➤ **Treated Set:**

Treated Set includes patients in entered set who have taken at least one dose of nintedanib.

Analysis for all primary and secondary outcomes will be done on treated set.

The following table defines the patient set is to be used for planned analysis.

Table 6.3: 1 Patient sets analyzed

Class of endpoints/outcomes	Patient set		
	Screened Set	Entered Set	Treated Set
Primary and key secondary outcomes (Safety)	-	-	X
(Other) Secondary and further outcomes	-	-	X
Demographic/baseline outcomes	-	X	-

Note: No key secondary and further outcomes mentioned in CTP.

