## **7.4 PRIMARY OUTCOME(S)**

- Incidence of all ADRs in nintedanib treated patients:

The frequency with percentages and incidence rate of all ADRs in nintedanib treated patients will be tabulated by system organ class and preferred term.

The incidence rate will be presented as rate per 100 patient years along with 95% confidence interval.

➤ Incidence of all SAEs in nintedanib treated patients:

The frequency with percentages and incidence rate of SAEs will be tabulated by system organ class and preferred term.

The incidence rate will be presented as rate per 100 patient years along with 95% confidence interval.

All analyses of AEs will be based on the number of patients with AEs and not on the number of AEs.

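### The planned percentages count patients with incomplete follow-up as event-free, and no visible analysis gives a censoring-adjusted 52-week risk beside the single rate per 100 patient-years

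*SAP*

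**What the plan says.** **Analysis set.** SAP 6.3: "Treated Set includes patients in entered set who have taken at least one dose of nintedanib", and "Analysis for all primary and secondary outcomes will be done on treated set". Protocol 10.1 agrees: "Patients who have taken at least one dose of nintedanib will be included in the safety analysis". Protocol 10.7 names a single ground for ineligibility, "Required registration procedure was not followed". The current text asks for no visit after visit 1.

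**Primary outcomes (SAP 7.4).** ADRs and SAEs are shown as numbers and percentages of patients, with a rate: "The incidence rate will be presented as rate per 100 patient years along with 95% confidence interval". The rate is patients with a first event divided by time at risk, with a Poisson interval. Patients without the event contribute time up to an end date that the section does not define.

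**Secondary outcome (SAP 7.5.2).** "Frequency and percentage of patients who require dose reductions, interruptions and discontinuation due to adverse events will be presented separately". SAP 7.8.1 adds the rate and its 95% interval for the same three event types.

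**Use.** SAP 3 makes one specification serve "a status report of the active surveillance to be submitted to DCGI annually and for the final analysis".

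**Handling of incomplete follow-up.** SAP 6.6 plans no missing-data analysis and imputes only AE onset dates. SAP 6.5 states that no statistical model is involved. SAP 7.7 summarises days on treatment and weeks of exposure. No visible section plans a Kaplan-Meier, cumulative-incidence or interval-specific estimate.

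**The concern.** Incomplete observation is foreseeable. Protocol 10.9 names loss to follow-up as a limitation, and at an annual cut-off recently enrolled patients necessarily have short follow-up. Those patients sit in the denominator of every percentage as if observed without an event, so the percentage is too low as an estimate of on-treatment risk to 52 weeks.

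The companion rate corrects for how long patients were observed, but one number over the whole window summarises the experience well only if the hazard is roughly constant. If first onsets cluster in the first weeks, the rate depends on how much later person-time has accrued. A regulator reading successive reports could then see the percentage rise and the rate fall with no change in the safety of the drug.

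**Working it through.** **No stated figure to reproduce.** On size, Protocol 10.5 says only "The sample size of 200 is as per the request from the regulatory agency". The SAP's exact interval is the standard exact Poisson interval: 20 cases in 150 patient-years give 13.3 (8.1 to 20.6) per 100. The formula is not at fault.

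**Inputs.** From the documents: N = 200, 52-week window, Treated Set denominator, first events over person-time. Assumed, because the documents give nothing: first-ADR hazard of 2.5 per year to week 12 and 0.4 per year after; loss of 0.2 per year; 5% with no follow-up; uniform entry over 2 years.

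**Step 1: true risk.** Week 12 = 84/365.25 = 0.2300 y; week 52 = 364/365.25 = 0.9966 y.
- Cumulative hazard = 2.5 × 0.2300 + 0.4 × 0.7666 = 0.8816.
- Risk = 1 − exp(−0.8816) = **58.6%**.

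**Step 2: crude percentage with loss of 0.2 per year.**
- To week 12: (2.5/2.7) × [1 − exp(−2.7 × 0.2300)] = 0.9259 × 0.4626 = 0.4283.
- After week 12: 0.5374 × (0.4/0.6) × [1 − exp(−0.6 × 0.7666)] = 0.5374 × 0.6667 × 0.3687 = 0.1321.
- Sum = **56.0%**. If a further 5% have no follow-up: 0.95 × 56.0% = **53.2%**.

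**Step 3: the same check with a constant hazard.** Take a true risk of 40% and 20% lost by week 52, with time in units of 52 weeks.
- Event hazard = −ln 0.6 = 0.511; loss hazard = −ln 0.8 = 0.223.
- Crude = (0.511/0.734) × (1 − 0.6 × 0.8) = 0.696 × 0.52 = **36.2%**.
- With 0, 10, 20, 30 and 40% lost: 40.0, 38.1, 36.2, 34.2 and 32.0%.
- For an early-loaded (Weibull, shape 0.5) hazard: 40.0, 38.8, 37.6, 36.2 and 34.8%.

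**Step 4: does stopping treatment cause the bias?** Simulation, N = 200, early-loaded hazard, 30% stopping as a competing event.

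| Lost | Crude | Aalen-Johansen |
|---|---|---|
| 0% | 36.3% | 36.3% |
| 20% | 34.2% | 36.2% |

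With nobody lost, the two agree. Only unobserved time creates the gap.

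**Step 5: the rate at annual reports** (hazards of step 1, uniform entry over 2 years, follow-up capped at 52 weeks, no loss).
- A fully followed patient contributes 0.5859 expected events and 0.5464 years at risk.
- Year 1: averaging over follow-up from 0 to 1 year gives 0.452 events and 0.3077 years, a rate of **147** per 100 patient-years.
- Year 2: half the patients are complete, so events = (0.452 + 0.586)/2 = 0.519 and years = (0.3077 + 0.5464)/2 = 0.4270, a rate of **122**.
- Year 3: 0.5859/0.5464, a rate of **107**.
- The crude percentages at the same reports are about 45, 52 and 59%.
- Under a constant hazard, events and person-time grow in proportion and the rate does not change. At a 40% risk it is 51.3 at every follow-up length.

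**The case against.** **The documents never claim a 52-week risk.** They speak of incidence and of estimating occurrence, and call the analysis descriptive. That stands: this is an unstated target and a missing analysis, not a miscalculation.

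**Follow-up is partly handled.** Person-time rates are planned for the primary events and, in SAP 7.8.1, for the secondary ones, and exposure is tabulated. That stands, but exposure tables cannot be turned into a corrected risk.

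**Deaths and stopping.** A reader might infer that patients who die or stop for other reasons also bias the percentage. They do not, for on-treatment risk with these as competing events: they rightly remain in the denominator (step 4).

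**Drift.** A reader might infer that the rates must appear to improve each year. The documents give no hazard shape, and drift needs a declining hazard. The assumed one falls about 6-fold (2.5/0.4). Comparing cohorts all followed for exactly 12 weeks with cohorts all followed for 52 weeks gives 250 against 107, a 2.3-fold fall, but no annual report has that structure. Staggered entry gives 147/107, about 1.4-fold. Group B patients bring retrospective data from treatment start (SAP 6.1), which would shrink it further, and the 52-week cap limits it.

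**Size against precision.** At N = 200 the 95% half-width at 58.6% is 1.96 × √(0.586 × 0.414/200) = 6.8 points. The shortfalls of 2.6 and 5.4 points lie within it. That stands, but the bias has a known direction and the interval does not allow for it.

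**What can be seen.** The SAP contents list has redacted entries and the CRF is not available, so absence is judged on visible text, and the recording of the reason for stopping nintedanib cannot be confirmed.

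**Conclusion.** The concern holds in a limited form. As written, the percentages in SAP 7.4 and 7.5.2 understate on-treatment risk to 52 weeks whenever patients are lost, unseen after visit 1, or still accruing at a data cut-off. In the illustration, 58.6% becomes 56.0% with loss alone and 53.2% with a further 5% unobserved. With complete follow-up there is no shortfall. The final analysis is affected only by loss and absent follow-up; the annual reports are also affected by accrual.

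The rate is a valid adjustment for length of observation, but it is not a risk. It falls with maturing follow-up only if onsets cluster early. All sizes rest on assumed hazards, loss and entry pattern. The documents do not support the stronger readings that the plan misreports a quantity it promised, that deaths and stopping bias the percentages, or that the rates will drift in any case.

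**What to change.** In SAP 7.4 and 7.5.2, for any ADR, any SAE, and each of AE-related dose reduction, interruption and discontinuation:

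- Add the 52-week cumulative incidence (Aalen-Johansen) with 95% confidence interval and numbers at risk.
- Censor at loss to follow-up or data cut-off, and define the end date of time at risk accordingly.
- Treat death and discontinuation of nintedanib as competing events. Where AE-related discontinuation is itself the outcome, only death and discontinuation for other reasons compete.
- Add rates for a pre-specified early and later interval, for example 0–12 and >12–52 weeks. The documents do not fix the cut-point, so it must be chosen in advance.
- Report the number of patients with incomplete follow-up, including those with no visit after visit 1.
- Keep the crude percentages as description.

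**Cost.** SAP wording and routine programming, built mainly on the start, first-event and end dates that SAP 7.4 already needs. Confirm that the CRF separates AE-related from other stopping. The downside is a few more tables and slightly less favourable headline percentages.

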## **7.7 EXTENT OF EXPOSURE**

Exposure to nintedanib will be estimated as time from the day nintedanib is initiated until 52 weeks or discontinuation of the drug (or the final contact with the patient for the last regular observation/end of the study)..

Days on treatment will be summarized using N, mean, SD, minimum, median, maximum, Q1 and Q3. Frequency and percentage will be presented for extent of exposure in weeks till Week 52.

## **7.8 SAFETY ANALYSIS**

Patients who have taken at least one dose of nintedanib will be included in the safety analysis.

In general, safety analyses will be descriptive in nature and will focus on any suspected ADRs (adverse drug reactions) associated with nintedanib and SAEs (serious adverse events) in patients exposed to nintedanib.

Additionally, physical examinations, vital signs, pulmonary function test, clinical laboratory test (including clinical biochemistry, liver function test (LFT), urinalysis, coagulation test, immunological test and arterial blood gas) etc. evaluations will be listed.

### **7.8.1 Adverse events**

Adverse events will be collected at the time points or visits specified in flowchart presented in the CTP. The medical records of patients belonging to Group B will be evaluated to see if any ADRs and SAEs have occurred in the nintedanib treated arm during the duration of the treatment before participation in the active surveillance. Group B and Group C patients will be followed up according to clinical practice as per the suggested visit. At each visit, all ADRs associated with nintedanib and SAEs will be recorded and reported.

No adverse events of special interest (AESI) have been defined for this active surveillance.

AEs will be coded using the current version of the Medical Dictionary for Regulatory Activities (MedDRA) version 20.0 or higher and will be based on the concept of treatment emergent AEs. All AEs occurring between first intake of nintedanib prescribed and up to 52 weeks or discontinuation of the drug (or the final contact with the patient for the last regular observation/end of the study) will be considered ‘treatment emergent’. Adverse event summaries will summarize only treatment emergent adverse events (TEAEs), which are defined as AEs not present prior to the nintedanib prescribed.

An AE is considered to be an ADR if either the physician who has reported the AE or the sponsor assesses its causal relationship (at least a reasonable possibility of a causal relationship) between event and drug checked as 'Yes'.

TEAEs will be categorized into one or more of the following categories depending on the type of events reported:

- All TEAEs
- All TEAEs by severity
- All SAEs
- Non-Serious TEAEs
- TEAEs leading to death
- All treatment related TEAEs
- All treatment related SAEs
- All treatment related Non-Serious TEAEs
- All treatment related TEAEs leading to death
- TEAEs leading to Treatment discontinuation
- TEAEs leading to dose reduction
- TEAEs leading to dose interruption

The frequency and incidence rate of AEs/SAEs and ADRs will be tabulated by system organ class and preferred term.

Multiple overlapping or adjacent AE occurrence of same AE are collapsed into one AE event according to BI standard [\(7\)](#).

Two AE are considered to be time-overlapping if the start date of the second, later occurrence is earlier or equal to the end date of the first occurrence.

Two AE are considered to be time-adjacent if the start date of the second, later occurrence is one day later than the end date of first occurrence.

Patients reporting more than one AE for a given MedDRA Preferred Term will be counted only once for that term using the most severe incident. Patients reporting more than one type

of event within a SOC will be counted only once for that SOC. Any deaths, other SAEs, and other significant adverse events, including those leading to premature discontinuation, will be separately identified.

All AEs will be listed individually for each patient by system organ class (SOC), preferred term (PT) and lowest level term (LLT) assigned to the AEs.

AE onset date should not have any missing value in year/month/day. If any missing dates issues, communicate it to data management first.

No imputation is planned for missing AE data except AE onset date. Missing AE onset dates will be handled according to BI standard [\(2\)](#).

All analyses of AEs will be based on the number of patients with AEs and not on the number of AEs.

An overall summary of adverse events will be presented.

The frequency of patients with adverse events (serious and non-serious adverse events), adverse drug reaction (serious and non-serious ADRs), adverse events leading to death, adverse drug reaction leading to death and other significant adverse events (according to ICH E3) will be summarized by primary system organ class and preferred term along with the incidence rate and its 95% confidence interval.

Adverse event leading to treatment discontinuation, treatment interruption and dose reduction will be separately summarized by primary system organ class and preferred term along with the incidence rate and its 95% confidence interval.

The system organ classes will be sorted by default alphabetically and preferred terms will be sorted by frequency in descending order within system organ class. Death due to adverse event will be listed separately.

According to ICH, other significant AE includes non-serious AE with action taken is either "dose reduced" or "drug withdrawn" or Trial Clinical Monitors classify non-serious AE as 'other significant' (e.g. marked hematological abnormality).

Duration of AE will be calculated as AE stop date - AE start date +1. Both start and stop dates need to be present to calculate a duration.

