10.7.1 Analyses of outcome events

All outcome events are based on reported AE data which will be handled according to BI standards (see the section below). In addition, patients for all analysis will be stratified by (i) no prior IPF treatment (ii) prior Pirfenidone treatment (switch) (iii) other prior treatment used for the management of IPF (switch) (iv) other prior treatment used for the management of IPF (add-on). In case of conflicting results the results of the first strata [(i) no prior IPF treatment] are decisive, because in new users potential bias is the smallest.

Safety:

In general, safety analyses will be descriptive in nature, and will be based on BI standards, and will focus on all ADRs and SAEs.

AEs will be coded using the current version of the Medical Dictionary for Regulatory Activities (MedDRA) and will be based on the concept of treatment emergent AEs. To this end, all AEs occurring between first intake of Nintedanib prescribed at visit 1 and up to 52 weeks/discontinuation will be considered 'treatment emergent'. An AE is considered to be an ADR if either the physician who has reported the AE or the sponsor assesses its causal relationship as 'related'.

The frequency and incidence of ADRs and SAEs will be tabulated by system organ class and preferred term.

No imputation is planned for missing AE data except for missing onset dates which will be handled according to BI standard.

Descriptive statistics will be calculated for laboratory tests, vital signs and physical examination.

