## **5 OUTCOMES**

### **5.1 PRIMARY OUTCOMES**

- Incidence of all ADRs in nintedanib treated patients
- Incidence of all SAEs in nintedanib treated patients

[figure not shown]

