## **6.6 HANDLING OF MISSING DATA AND OUTLIERS**

No missing data analysis is planned for this study. Missing values will be considered as missing, no imputation will be done for the analysis purpose.

No imputation is planned for missing AE data except for missing or incomplete AE onset dates which will be imputed according to BI standards  (i.e. “Handling of missing and incomplete AE dates”) as below.

Step 1: For each missing / incomplete AE onset date, an interval (INT\_START, INT\_END) is defined. The true unknown analysis start date of AE is assumed to be within the interval.

Scenario of AE onset date	INT_START	INT_END
Completely missing AE onset date	Min (AE end date, Date of informed consent)	Min (AE end date, Date of last visit)

Scenario of AE onset date	INT_START	INT_END
Only year of AE onset date is non-missing	Min (AE end date, 01 JAN of the reported year)	Min (AE end date, 31 DEC of the reported year)
Only year and month of AE onset date is non-missing	Min (AE end date, 01 of the reported month)	Min (AE end date, Last date of the reported month)

Note: Completely missing AE end date will not be considered in this derivation step.

Partially missing AE end date will be temporarily assigned the largest possible date in the observed year or month in the derivation step.

Step 2: Derive an imputed AE onset date based on the interval from step 1.

Scenarios	TESS/ Non-TESS	Imputed AE onset date
1. Date of first drug administration is within the interval [INT_START, INT_END]	TESS	Date of first drug administration
2. Date of first drug administration is before INT_START*	TESS	INT_START from step 1
3. Date of first drug administration is after INT_END or missing	Non-TESS	INT_END from step 1

TESS- Treatment emergent AE

\*Note: If INT\_START is after the date of the last drug administration plus residual effect period, then the AE is non-TESS.

Step 3: The AE onset date imputation flag(s) are set according to the level of imputation performed and the standard CDISC rules for imputation or the legacy data imputation rules.

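### SAP 7.8.1 gives two inconsistent definitions of treatment-emergent AE; the narrower one, absent from the protocol, could be programmed to drop worsening or recurrence of conditions recorded at baseline

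*SAP*

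**What the plan says.** Protocol 10.7.1 uses a time window alone. Treatment-emergent events are "all AEs occurring between first intake of Nintedanib prescribed at visit 1 and up to 52 weeks/discontinuation".

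SAP 7.8.1 first repeats that window: "All AEs occurring between first intake of nintedanib prescribed and up to 52 weeks or discontinuation of the drug", with final contact or end of study as a further end point. The next sentence then says "Adverse event summaries will summarize only treatment emergent adverse events (TEAEs"), "which are defined as AEs not present prior to the nintedanib prescribed". The section goes on to list TEAE categories. These include all SAEs, treatment-related events, and events leading to discontinuation, dose reduction or interruption.

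The primary SAE outcome in SAP 5.1 is "Incidence of all SAEs in nintedanib treated patients". For its analysis SAP 7.4 says "The frequency with percentages and incidence rate of SAEs will be tabulated by system organ class and preferred term" and states no treatment-emergence filter of its own. SAP section 4 declares no change from the analysis planned in protocol version 5.0.

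**The concern.** The two sentences are different tests. One asks when the event occurred. The other asks whether the AE was absent beforehand, and it is the one attached to what will be summarised. It does not say how to treat an event that worsens or recurs on drug.

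This matters because the study exists only to estimate safety incidence. Every patient has IPF at entry (protocol 10.2.2.1, inclusion criterion 1). Protocol 10.3.3 also collects a long baseline history, including pneumonia, respiratory failure, pulmonary embolism, reflux disease and hypertension. If a programmer took the second sentence literally and checked AEs against that history, on-treatment worsening or recurrence of a listed condition could be left out of the summaries. That would understate the primary SAE and ADR incidence, and also the secondary percentages for dose reduction, interruption and discontinuation.

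**Working it through.** There is no figure in the plan to reproduce. The sample size of 200 is a regulatory request (protocol 10.5), and no expected SAE rate is given. The check is therefore a comparison of the texts, followed by an illustration of scale.

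**1. The rules side by side**

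| Place | Test for treatment emergence | Looks at prior presence? |
|---|---|---|
| Protocol 10.7.1 | Occurs from first intake to 52 weeks/discontinuation | No |
| SAP 7.8.1, window sentence | Same, with final contact/end of study added | No |
| SAP 7.8.1, following sentence | AE not present before nintedanib | Yes |
| SAP 6.6, missing or partial onset dates | Onset interval against first dose, e.g. "Date of first drug administration is before INT_START" | No |
| SAP 7.4, time at risk | Treatment start to start date of the first specific AE | No |

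Only one of the five looks at prior presence.

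**2. Can it reach the primary tables?** SAP 7.4 states no filter, but SAP 7.8.1 restricts AE summaries to TEAEs, lists all SAEs among the TEAE categories, and describes the same tabulation by system organ class and preferred term. So it can. The secondary outcome is exposed in the same way through the categories for discontinuation, reduction and interruption.

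**3. Could it be programmed as an exclusion?** Protocol 12.2 collects ADRs and SAEs only from initiation of nintedanib, so few AE records should predate the drug. The second sentence is then either largely redundant or points to the baseline history. Comorbidities are recorded with start, stop or ongoing dates (protocol 10.3.3). Medical history and AEs are both coded in MedDRA 20.0 or higher (SAP 7.2 and 7.8.1). A match on preferred term is feasible, although no section asks for one.

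**4. Scale, on assumed inputs.** Assume N = 200, a constant hazard, full follow-up of T = 364/365.25 years and no dropout. Assume also that a patient whose event is dropped has no other SAE. Let c be the patients counted and p = c/N.

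- Hazard: λ = −ln(1 − p)/T. Patient-years: PY = c/λ.
- Rate (SAP 7.4): 100 × c/PY.
- Exact limits (SAP 7.4): 100 × χ²(0.025; 2c)/(2PY) and 100 × χ²(0.975; 2c + 2)/(2PY).

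For a 30% SAE risk with all events counted, c = 60, λ = 0.3567/0.9966 = 0.358 and PY = 60/0.358 = 167.6.

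| Share of SAE patients dropped | c | PY | Rate per 100 PY (95% CI) | Fall |
|---|---|---|---|---|
| 0% | 60 | 167.6 | 35.8 (27.3 to 46.1) | – |
| 10% | 54 | 171.0 | 31.6 (23.7 to 41.2) | 12% |
| 30% | 42 | 177.6 | 23.7 (17.0 to 32.0) | 34% |
| 50% | 30 | 184.0 | 16.3 (11.0 to 23.3) | 54% |

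Dropping 50% takes the rate from 22.4 to 10.6 at a 20% risk, and from 51.3 to 22.4 at a 40% risk. The rate falls by more than the share dropped because a patient whose event is removed contributes more time at risk. Under the window rule nothing changes.

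**The case against.** A reader might infer that the SAP excludes worsening of IPF, and of other existing disease, from the primary SAE incidence. The documents do not support that.

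- The clause concerns AEs, not diseases, that were present before. Protocol 12.1 defines an AE as any untoward occurrence and an SAE by its result. An on-treatment hospitalisation or death from IPF is a new event with its own onset, and no section excludes it.
- The window sentence immediately before makes every AE in the period treatment emergent. The second sentence can be read as loose shorthand for it, and SAP 6.6 and 7.4 work on dates alone.
- SAP 7.8.1 lists all AEs individually, lists deaths due to AEs separately, and requires deaths and other SAEs to be separately identified. Fatal events would stay visible in the report.
- Safety analysis follows sponsor standards that are cited but not reproduced, and these may settle how TEAEs are programmed.

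A reader might also infer that the second sentence starts the clock at the date of prescription. More probably the phrase simply names the drug, since both window sentences use similar wording after first intake.

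These points stand, and they rule out a definite exclusion. They do not remove the conflict. The narrower sentence is the one tied to the summaries, it has no counterpart in the protocol, and it does not say what happens to a recurring term. A patient with earlier pneumonia or respiratory failure may have the same preferred term in the history, so the distinction between AE and disease does not settle every case.

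**Conclusion.** The point holds as an internal contradiction that should be corrected. SAP 7.8.1 carries two definitions of treatment emergence. The narrower one departs from protocol 10.7.1 without being declared, and it can reach the primary and secondary safety tables. Whether it would remove any event depends on how it is programmed.

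The size of the effect cannot be known from the documents. The SAE risk, the shares dropped, the constant hazard and the complete follow-up are all assumptions. The falls of 12% to 54% at a 30% risk show only that a literal application could matter. They do not predict the result.

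**What to change.** Delete the second definition in SAP 7.8.1 and keep one rule aligned with protocol 10.7.1. Suggested text: *A reported AE is treatment emergent if its onset, or a worsening reported as an AE with its own onset date, falls on or after first intake of nintedanib and within the stated window, regardless of medical history.*

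Worsening should be counted as reported, not derived against baseline, because protocol 10.3.3 records comorbidities with dates but no general severity grade. Under the AE definition in protocol 12.1, a reported worsening in the window already qualifies, so this clarifies the protocol and does not change it.

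Apply the same rule in SAP 6.6, 7.4, 7.5.2 and 7.8.1. In 6.6, the note on a residual effect period should be reconciled with the window in 7.8.1, which does not mention one. A statement in 7.4 that this rule defines the events counted would close the gap for the primary tables.

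The cost is one replaced sentence and a few cross-references, with no new data.
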